## 8. SAFETY ANALYSES

All participants enrolled and administered any TAF/EVG insert will be assessed for safety.

### 8.1 Primary Safety Analyses

The primary safety endpoint is defined as follows:

All Grade 2 and higher AEs

The number and the percentage of participants experiencing each safety endpoint will be tabulated by dosing regimen (one insert or two inserts). This table will display a summary for any primary safety endpoint and for each individual safety endpoint. Each participant will contribute once in each category

(i.e., only for highest severity AE for each participant) for the calculation of event rates for each dosing regimen. Exact binomial confidence intervals (Clopper-Pearson) will be calculated for each safety endpoint, even if no events occur for an endpoint for a particular dosing regimen.

## 8.2 Adverse Events

Summaries of adverse events will include a cumulative listing of adverse events, a table displaying the total number of adverse events by severity grade and relationship to study product, a table of the incidence of adverse events by MedDRA organ system class/preferred term and severity, and a table of incidence of adverse events by MedDRA organ system class/preferred term and relationship to study product. Tables will be displayed by dosing regimen, and listings will include the dosing regimen when the AE occurred.

## 8.3 Laboratory Evaluations

The number and percentage of participants with a positive result for the following laboratory tests will be displayed in a table overall and by site: hCG for pregnancy and HIV. A listing of participants with positive results of STI testing (syphilis, trichomonas, gonorrhea, chlamydia) after dose administration will be presented.

Hematology results after dosing with each regimen, including hemogram (hemoglobin, hematocrit, MCV, platelets, WBC) and differential (neutrophils, lymphocytes, monocytes, eosinophils, and basophils) results will be tabulated by dosing regimen using descriptive statistics.

Serum chemistries (AST, ALT, and creatinine) after dosing with each dosing regimen will be tabulated by dosing regimen using descriptive statistics.

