**Table 14: Other Post-Dosing Visits**

Other Post-Dosing Visits - Visits 5, 6, 9, and 10		
Component	Procedures	
Administrative and Regulatory	
 
Review/update locator information
 
Provide reimbursement
 
Schedule next visit/contact
 
	
Behavioral/Counseling	
 
HIV pre- and post-test counseling*
 
HIV/STI risk reduction counseling*
 
Protocol counseling
 
Behavioral In-Depth Interview (IDI) (Visit 10 only)
 
	
Clinical	
 
Review/update medical history
 
Review/update concomitant medications
 
Perform targeted physical examination*
 
Perform genital examination*
 
Perform pelvic examination* ▲
 
Perform rectal examination
 
Treat or prescribe treatment for RTI/UTI, or STIs*
 
Provide available test results
 
Collect/update AEs
 
	
Laboratory	Pharyngeal	
 
NAAT for GC/CT*
 

	Urine	
 
NAAT for GC/CT* ▼
 
Urine dipstick/culture*
 
Pregnancy test* ■
 

	Blood	
 
CBC with differential and platelets* (required at Visit 10)
 
Chemistries (AST/ALT/creatinine)* (required at Visit 10)
 
Syphilis serology*
 
HIV-1/2 test* (required at Visit 10)
 
Blood for PK
 

	Pelvic ▲	
 
CVF for PK △
 
CVF for PD △
 
NAAT for GC/CT/TV*
 

	Anorectal	
 
• Rectal fluid for PK △
 
• Rectal fluid for PD △
 
• Rectal enema prior to biopsy collection △
 
• Rectal tissue for PK △
 
• Rectal tissue for PD △
 
• NAAT for GC/CT*
 

Study Product/Supplies		
 
• Offer condoms
 
• Provide home enema kit (Visit 6 only)
 

\* If indicated ▲ Participants assigned female sex at birth and if anatomy allows ▼ If pelvic GC/CT cannot be performed ■ Participants of childbearing potential

△ Group 1 will have biopsies, rectal fluid and cervicovaginal fluid (if applicable) collected at 48 hours (Visits 5 and 9) following each administration of product;

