### **8.3 Adverse Events Definitions and Reporting Requirements**

#### **8.3.1 Adverse Events**

An AE is defined as any untoward medical occurrence in a clinical research participant administered an investigational product and which does not necessarily have a causal relationship with the investigational product. As such, an AE can be an unfavorable or unintended sign (including an abnormal laboratory finding, for example), symptom or disease temporally associated with the use of an investigational product, whether or not considered related to the product. This definition is applied to all study groups, and is applied to all groups beginning at the time of enrollment (i.e., once a participant is randomized) through the termination visit. The term “investigational product” for this study refers to the TAF/EVG Insert, 20/16 mg.

Study participants will be provided instructions for contacting the study site to report any untoward medical occurrences they may experience. In cases of potentially life-threatening events, participants will be instructed to seek immediate emergency care. Where feasible and medically appropriate, participants will be encouraged to seek evaluation where a study clinician is based, and to request that the clinician be contacted upon their arrival. With appropriate permission of the participant, whenever possible, records from all non-study medical providers related to untoward medical occurrences will be obtained and required data elements will be captured in the study database. All participants reporting an untoward medical occurrence will be followed clinically until the occurrence resolves (returns to baseline) or stabilizes.

Study site staff will document in source documents and in the study database all AEs reported by or observed in enrolled study participants regardless of severity and presumed relationship to study product. AE severity will be graded per the DAIDS Table for Grading Adult and Pediatric Adverse Events, Corrected Version 2.1, July 2017 and/or Addenda 1, 2 and 3 (Female Genital [Dated November 2007], Male Genital [Dated November 2007] and Rectal [Clarification Dated May 2012] Grading Tables for Use in Microbicide Studies).

Please note:

- Asymptomatic BV and asymptomatic candidiasis will not be reportable AEs;  
*Note:* Asymptomatic BV and asymptomatic candidiasis will be captured on the CRF that captures STI results.

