## 10.4 Sample Size and Power Calculations

### Safety Endpoints

The proposed total sample size for assessing safety is approximately N=20 participants. This sample size is based upon the size of similar Phase 1 studies of microbicides for HIV prevention.

As a means to characterize the statistical properties of this study, [Table 17](#) below presents the probability of observing zero, at least one, and two or more safety endpoints among the 20 participants for various “true” event rates:

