**Figure 1: MTN-039 Study Visit Schedule**

As displayed in Figure 1, participants will receive a rectally administered dose of one TAF/EVG insert at Visit 3 and have safety laboratory tests, PK and PD assessments performed over the next three days (Visits 4, 5, and 6). Participants will self-administer a saline enema at home the evening prior to a clinic dosing visit (Visits 3 and 7). After a washout period of one to seven weeks following the last tissue sampling associated with one TAF/EVG insert dosing, participants will receive dosing of two TAF/EVG inserts at Visit 7 and have safety laboratory tests, PK and PD assessments performed over the next three days (Visits 8, 9, and 10). A final study contact will occur approximately 3-7 days after Visit 10 and may be conducted over the phone.

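### No CBC or chemistry panel is required after the one-insert dose, yet SAP 8.3 tabulates laboratory results by dose and SAP 8.1 gives both doses the same denominator

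*SAP*

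**What the plan says.** **Schedule.** The protocol requires CBC and AST/ALT/creatinine at Screening (Table 10). It marks them as done only if indicated at Enrollment (Table 11), the dosing visits (Table 12), the 24-hour visits (Table 13) and Visit 11 (Table 15). For Visits 5, 6, 9 and 10, Table 14 has "CBC with differential and platelets* (required at Visit 10") and "Chemistries (AST/ALT/creatinine)* (required at Visit 10"). Appendix I shows the same pattern.

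**SAP description.** SAP 2.1 says that after one insert participants "have safety laboratory tests, PK and PD assessments performed over the next three days (Visits 4, 5, and 6"). It says the same of Visits 8, 9 and 10 after two inserts.

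**SAP analysis.** Section 8.3: "Serum chemistries (AST, ALT, and creatinine) after dosing with each dosing regimen will be tabulated by dosing regimen using descriptive statistics". Section 8.1, on the primary safety endpoint of AEs at Grade 2 or above: "The number and the percentage of participants experiencing each safety endpoint will be tabulated by dosing regimen (one insert or two inserts"), with Clopper-Pearson intervals even where no events occur. Section 6.2 runs the one-insert window from Visit 3 dosing to just before Visit 7 dosing. Section 3.2 drops a participant from a dose only if that dose was not given.

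**Definitions and precision.** Under Protocol 8.3.1, "an AE can be an unfavorable or unintended sign (including an abnormal laboratory finding, for example"). Protocol 10.4 says: "The proposed total sample size for assessing safety is approximately N=20 participants". It quotes a 16.8% upper bound for zero events in 20 at either dose.

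**The concern.** The SAP reads as if both doses had scheduled safety laboratory tests. The protocol schedule gives the one-insert dose none.

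- **Laboratory tables.** The by-dose tables in SAP 8.3 would set whoever happened to be tested after one insert beside nearly everyone after two. A difference between the columns, or the lack of one, could reflect who was tested.
- **Primary endpoint.** An asymptomatic change in ALT, creatinine or blood count can be an AE. After one insert it is found only if someone orders the test. In SAP 8.1, participants who were dosed but not tested stay in the denominator and count as free of laboratory events.
- **Attribution.** No panel is required at Visit 7. A change that began after one insert and persisted could first appear at Visit 10 and be credited to two inserts. Dose order is fixed, so the design cannot separate the two explanations.

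**Working it through.** **1. Reproduce the protocol's figures (10.4, Tables 17 and 18).** With n = 20:

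- P(at least one event) at a true rate of 5% = 1 − 0.95^20 = 64.2%, as stated. At 10% it is 1 − 0.90^20 = 87.8%, as stated.
- Exact two-sided 95% upper bound for 0/20 = 1 − 0.025^(1/20) = 16.8%, as stated.

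Both assume that all 20 participants are assessed for the event.

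**2. Count required panels by attribution window.**

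| Window | Visits | Required CBC/chemistry panels |
|---|---|---|
| Before dosing | 1, 2 | 1 (Screening) |
| One insert | 3 (after dosing) to 7 (before dosing) | 0 |
| Two inserts | 7 (after dosing) to 11 | 1 (Visit 10) |

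The step 1 figures can therefore hold for laboratory-detected events after two inserts if all 20 attend Visit 10. After one insert the number tested is unspecified.

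**3. Effect on detection.** Let q be the share of one-insert laboratory events that if-indicated testing picks up. The documents give no value for q, so it is varied. The true rate of 5% is a row of Table 17, not an estimate for this product. P(at least one in 20) = 1 − (1 − 0.05q)^20.

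| q (assumed) | Expected observed rate | P(at least one seen) |
|---|---|---|
| 1 | 5% | 64.2% |
| 0.5 | 2.5% | 39.7% |
| 0.25 | 1.25% | 22.2% |
| 0.1 | 0.5% | 9.5% |
| 0 | 0% | 0% |

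**4. Effect on the interval.** If m participants are tested after one insert and none has an event, the upper bound is 1 − 0.025^(1/m). Again m is assumed.

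| m (assumed) | Upper bound for 0/m |
|---|---|
| 20 | 16.8% |
| 15 | 21.8% |
| 10 | 30.8% |
| 5 | 52.2% |
| 2 | 84.2% |
| 0 | not estimable |

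These bounds treat the tested as a random subset. Testing on indication is not random, so they show the loss of information and are not valid limits for all participants.

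**5. Length of the AE windows.** Protocol 7.4.1 places Visit 7 one to seven weeks after the last tissue sampling for Dose 1, which is at 48 hours in Group 1 and 72 hours in Group 2. The one-insert window thus runs from about 2 + 7 = 9 days to 3 + 49 = 52 days. After two inserts, Visit 10 is at 3 days and the final contact 3 to 7 days later, giving about 6 to 10 days. This inequality affects clinical AEs as well.

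**The case against.** **The protocol text may not be the latest.** Letters of Amendment 01 to 03 are not in the supplied documents. Letter 04 strikes a bullet on TFV in tissue homogenates that the base protocol does not contain, so an earlier letter had already changed the protocol. If one of them required panels after one insert, the conflict disappears. This stands, and it is why the letters come first in the fix. Letter 04 itself leaves the laboratory schedule alone.

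**Only some AEs are affected.** AE collection, history and rectal examination take place at every dosing and post-dose visit for both doses (Tables 12 to 14). This stands: the schedule gap concerns asymptomatic, laboratory-detected events.

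**No formal dose comparison is planned.** This is true (Protocol 10.7.2, SAP 2.5), so no test is invalidated. But Protocol 10.7.2 allows the doses to be compared descriptively on safety events and laboratory measurements, and SAP 8.1 specifies an interval for each dose.

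**The SAP already has some of the tools.** Section 5 provides for change from baseline, and 6.1.5 tabulates procedure completion. These help, but neither puts the number tested into the 8.3 tables nor changes the 8.1 denominator.

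**Stronger readings to avoid.** A reader might infer that laboratory events after one insert cannot be detected at all. The documents say if indicated, so zero detection is only the lower end of an unknown range. A reader might also infer that the whole by-dose primary endpoint is invalid, or that panels must be added after one insert. Neither follows: symptomatic AEs are sought at visits after both doses, and the documents conflict without showing which schedule was intended.

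**Conclusion.** On the supplied text, SAP 2.1 and the protocol's laboratory schedule disagree, and the by-dose analyses in SAP 8.3 and 8.1 do not allow for it. Required post-dose panels number zero in the one-insert window and one in the two-insert window. For asymptomatic laboratory AEs of Grade 2 or higher at an illustrative true rate of 5%, the chance of seeing at least one after one insert lies anywhere from 0% to 64%, and is about 40% if half are detected. The 16.8% upper bound for 0/20 is arithmetically right, but it does not apply to laboratory-detected events after one insert.

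This distorts description and the reading of intervals, and leaves no test invalid. It rests on two conditions: that no earlier letter of amendment required panels after one insert, and that not everyone was tested in that window anyway. The detection shares are assumptions.

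**What to change.** 1. Check Letters of Amendment 01 to 03 for any change to the laboratory schedule, then reconcile SAP 2.1 with the schedule in force. If a letter did require panels after one insert, cite it and show the number tested per dose.
2. If no panel was required after one insert, change SAP 8.3 to a paired Screening-to-Visit 10 summary, show the number tested per dose, and list one-insert results without summarising them. Say that this change spans both doses.
3. In SAP 8.1, show laboratory-detected and clinically detected Grade 2 and higher AEs separately. Use the number tested as the denominator for laboratory-detected events, noting that after one insert this describes only those tested. Do not attribute an abnormality first seen at Visit 10 specifically to two inserts.
4. State the unequal laboratory testing as a limitation, together with the unequal AE windows (about 9 to 52 days against about 6 to 10 days). Restricting the dose contrast to clinical AEs does not by itself equalise ascertainment.

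The cost is SAP wording and a few table columns, with no extra tests or visits. Adding panels would be a monitoring decision on which this point takes no view. It also looks too late: the SMC review was in December 2020 and SAP version 2.0 is dated October 2021.

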## 8.4 Other Safety Measures

Additional safety summaries include:

A listing of participants with abnormal findings on pelvic examination or rectal examination after dose administration (with dosing regimen when finding occurred) will be presented.

Concomitant medications are defined as any medication taken during the study. A participant listing of all concomitant medications will be presented.

## 9. PHARMACOKINETIC ANALYSES

Descriptive statistics will be used to summarize actual PK sample collection times (from dose administration) for blood, rectal fluid, rectal tissue, and cervicovaginal fluid samples, and these summaries will be provided by site and overall.

For each dosing regimen, blood samples are expected to be collected from all participants at baseline and at 1h, 2h, 4h, 6h, 24h, 48h, and 72h after dose administration. Samples of rectal fluid and cervicovaginal fluid (if applicable) are expected to be collected at the following study time points after dose administration: 2h, 4h, 6h, 24h, 48h, and 72h with samples collected for each participant only at specific time points based upon their group status (see table below). Similarly, samples of rectal tissue are expected to be collected at the following study time points after dose administration: 2h, 24h, 48h, and 72h with samples collected for each participant only at specific time points based upon their group status (see Table 1 below).

Table 1: Expected PK Sample Collection by Study Time Point

PK Specimen Type	Baseline Visit 2	1h, Visits 3 & 7	2h, Visits 3 & 7	4h, Visits 3 & 7	6h, Visits 3 & 7	24h, Visits 4 & 8	48h, Visits 5 & 9	72h, Visits 6 & 10
Blood	G12	G12	G12	G12	G12	G12	G12	G12
Rectal fluid			G1	G2	G1	G2	G1	G2
Rectal tissue			G1			G2	G1	G2
Cervicovaginal fluid			G1	G2	G1	G2	G1	G2

NOTE: G1=Group 1, G2=Group 2, G12=Groups 1 and 2.

A table summarizing the number and percentage of blood, rectal fluid, rectal tissue, and cervicovaginal fluid samples collected outside of the windows of the expected time points will be provided overall and by site. For samples collected outside of the window, a listing of sample collection times along with the amount of time before (-) the window or after (+) the window will be provided.

Allowable windows for the collection of blood, rectal fluid, rectal tissue, and cervicovaginal fluid are detailed in the MTN-039 SSP Manual in section 5.4.2 and Table 5-1 Sample Collection Time-Points Post-Insert Administration (and provided below).

**Table 5-1: Sample Collection Time-Points Post-Insert Administration**

Study Visit	Blood Samples (All time-points required for all participants)	Rectal/Pelvic Samples (per sample collection sequence assignment)
Enrollment	1 time during visit (no specified time; no dose administration)	1 time during visit (no specified time; no dose administration)
Dosing Visit (V3 and 7)	1 hours 2 hours 4 hours 6 hours (+/- 15-minute window permitted for hourly times)	Group 1: 2 and/or 6 hours  Group 2: 4 hours (+/-30 minute window permitted)
24-Hr Post-Dose Visit (V4 and 8)	24 hours (+/- 2 hours window permitted)	Group 2 only (+/- 2 hours window permitted)
48-Hr Post-Dose Visit (V5 and 9)	48 hours (+/- 4 hours window permitted)	Group 1 only (+/- 4 hours window permitted)
72-Hr Post-Dose Visit (V6 and 10)	72 hours (+/- 6 hours window permitted)	Group 2 only (+/- 6 hours window permitted)

## 9.1 Methods for Handling Missing and BLOQ Data

Each bioanalytical assay for blood, rectal fluid, rectal tissue, and cervicovaginal fluid has an assay sensitivity described by a lower limit of quantitation (LLOQ). These LLOQs will be reported for each matrix. Concentration values assayed below the LLOQ, as well as those classified as “Not Detected”, are identified as below the limit of quantitation (BLOQ).

In individual participant data listings, actual concentration values below the LLOQ will be displayed, if provided from the lab, along with the LLOQ for the assay. For values identified as BLOQ in the data, a listing will be provided displaying the assay and time point(s) of the BLOQ values.

Baseline samples that are BLOQ or missing will be assigned a numerical value of zero for the calculation of area under the concentration-time curve (AUC). Baseline samples that are missing will be excluded from the concentration summary calculations at baseline. Any anomalous quantifiable concentration values (at or above the LLOQ) observed at baseline will be identified in the study report and used for the computation of AUC.

Any other BLOQ concentrations that precede quantifiable samples in the initial portion of the profile or a BLOQ value that occurs between quantifiable data points, especially prior to  $C_{max}$ , will be evaluated to determine if an assigned concentration of zero makes sense, or if reanalysis or exclusion of the data is warranted. Following  $C_{max}$ , BLOQ values embedded between two quantifiable data points will be treated as missing when calculating AUC. If BLOQ values occur at the end of the collection interval (after the last quantifiable concentration), these will be treated as missing data. If consecutive BLOQ concentrations are followed by quantifiable concentrations in the terminal portion of the concentration curve, these quantified values will be excluded from the PK analysis by assigning them a value of missing, unless otherwise warranted by the concentration-time profile.

Drug concentration-time data will be listed for each participant and summarized by descriptive statistics at each nominal collection time. BLOQ concentrations will be treated as zero for computation of descriptive statistics. Concentrations assigned a value of missing will be omitted from the calculation of descriptive statistics. If the calculated mean concentration is BLOQ, the mean value will be reported as BLOQ, and SD will be reported as ND (not determined). Median, quartiles, minimum and maximum may be reported, and if any of these values are BLOQ, they will be reported as BLOQ.

When a concentration of zero cannot be plotted, the concentration may be assigned the value of LLOQ divided by 2 so that it may be displayed.

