### Oral TAF

A single-center, open-label, dose-ranging PK study investigated a single TAF dose in 24 healthy, premenopausal HIV seronegative female volunteers 18-49 years old. They were given 5, 10 or 25mg of TAF and each participant provided plasma, PBMC and cervical, vaginal and rectal tissue samples over 14 days. For each group, median (IQR) tenofovir plasma AUC0-14 days was 52.8 (49.5-59.6), 78.1 (68.2-86.9) and 169.7 (131.2-211.4) ng-h/mL and tenofovir-dp PBMC AUC0-14 days was 2268 (1519-4090), 4584 (3113-5734) and 9306 (6891-10785) fmol-h/106 cells, respectively. Tenofovir was quantifiable in 52% and 92% of FGT and GI tissues, whereas tenofovir-dp was quantifiable in only 5% and 19% of female genital tract and lower gastrointestinal tissues, respectively. Plasma tenofovir and PBMC tenofovir-dp were dose proportional (90% CI 0.87-1.15 and 0.62-1.02, respectively).

In a study of safety, antiviral activity, and pharmacokinetics of TAF, non-cirrhotic, treatment-naïve subjects with chronic hepatitis B were randomized (1:1:1:1) to receive TAF 8, 25, 40, or 120 mg, or TDF 300 mg for 28 days and assessed for safety, antiviral response, and pharmacokinetics, followed-up by off-treatment for 4 weeks. Following single dose administration on day 1, concentrations of TAF in plasma increased in proportion to dose, reaching maximum concentrations within 30-40 minutes. Consistent with the short elimination half-life of TAF (<45 min), plasma concentrations of the drug were below the limit of quantification 6-8 hours following dosing. TAF was completely undetectable in trough (pre-dose) plasma samples, collected over the 28 day dosing period. At each of the dose levels evaluated, mean plasma TFV concentrations following administration of TAF were substantially lower than those following TDF dosing. Relative to the mean TFV exposure (AUCinf) with TDF 300 mg (2267 ng-h/ml), percentage reductions in mean TFV exposures for TAF of 97%, 92%, 81%, and 33%, were seen following TAF doses of 8, 25, 40, and 120 mg, respectively.

In another study of pharmacokinetics, safety and antiviral activity of 40 or 120 mg of TAF compared with 300 mg of TDF, TAF and TDF were administered as monotherapy once daily for 14 days in 30 HIV-1-infected, treatment-naïve subjects. Administration of 40 mg

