## **2.5 Sample Size and Power**

The study is designed for a total accrual of twenty (20) participants, which gives sufficient power for the detection of adverse events as described in the protocol. Descriptive safety analyses and pharmacokinetic analyses are planned with no formal statistical testing.

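### SAP 9.1 gives conflicting rules for BLOQ values after the last quantifiable concentration, so the 24–72 h primary concentration summaries and their n depend on which rule is applied

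*SAP*

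**What the plan says.** SAP 9.1 has two parts that bear on late samples.

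The first goes through an individual profile from baseline to the terminal portion:

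- After Cmax, "BLOQ values embedded between two quantifiable data points will be treated as missing when calculating AUC". This is limited to AUC.
- The next sentence has no such limit: "If BLOQ values occur at the end of the collection interval (after the last quantifiable concentration), these will be treated as missing data".
- For quantified results that follow consecutive BLOQs in the terminal portion, "these quantified values will be excluded from the PK analysis by assigning them a value of missing". A closing qualifier lets the analyst depart from this where the profile justifies it.

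The second part covers descriptive statistics at each nominal time:

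- The rule for BLOQ results, with no exception for trailing ones, is: "BLOQ concentrations will be treated as zero for computation of descriptive statistics".
- The rule for values that have been set to missing comes directly after it: "Concentrations assigned a value of missing will be omitted from the calculation of descriptive statistics".
- On the order statistics it adds: "Median, quartiles, minimum and maximum may be reported, and if any of these values are BLOQ, they will be reported as BLOQ". A mean that falls below the LLOQ is likewise reported as BLOQ.

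SAP 2.2 and 9.2 make concentrations in blood, rectal fluid and rectal tissue the primary PK endpoints, tabulated by time point. SAP 9.2 calculates individual PK parameters for blood only.

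**The concern.** A trailing BLOQ result meets two instructions. If it has become missing, it drops out of the table. If it is BLOQ, it enters as zero. The SAP does not say which comes first, and late samples are where trailing BLOQ is most likely.

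The choice changes the primary 24, 48 and 72 h summaries and the n beside them. It also changes the confidence intervals that SAP 9.2 plans at each time point. Protocol 2.8.2 sets tissue benchmarks for EVG and TFV-DP, and readers will look at the late time points to judge how long levels persist. A mean over only those participants who still have measurable drug answers a different question from a mean over everyone sampled.

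The rule on late quantified values is a second, separate issue. Its wording matches the omission sentence, so real measurements leave the summaries by default.

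**Working it through.** **No figure to reproduce.** The documents give no numerical result for BLOQ handling, no LLOQ, no expected BLOQ fraction and no between-participant variability.

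**Inputs**

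- Blood: n = 20 ("The study is designed for a total accrual of twenty (20) participants", SAP 2.5).
- Rectal fluid and tissue: about 10 per sampling group. This assumes a 1:1 split, since the ratio is not stated.
- BLOQ fraction f = k/n at a time point: assumed, 30 to 80%.
- Concentrations: assumed lognormal. Main case CV 100%, so log-SD s = √ln(1 + 1²) = 0.833. Range 0.5 to 1.5.

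**Step 1: the two rules against each other.** Let S be the sum of the quantified values. Omission gives S/(n−k) and the zero rule gives S/n, so the ratio is n/(n−k), whatever the distribution.

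- 30% BLOQ: 20/14 = 10/7 = 1.43
- 50% BLOQ: 20/10 = 10/5 = 2.0
- 80% BLOQ: 20/4 = 10/2 = 5.0

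If every value at a time point is trailing BLOQ, omission leaves n = 0 and no summary. The zero rule reports BLOQ with full n.

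**Step 2: each rule against the true value.** Set LLOQ = 1 and let z(p) be the standard normal quantile. Then:

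- zero-rule mean / true mean = Φ(s − z(f))
- omission mean / true mean = Φ(s − z(f)) / (1 − f)
- omission median / true median = exp{s · z((1 + f)/2)}

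With s = 0.833:

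| BLOQ | Φ(s − z(f)) | Zero rule: mean/true | Omission: mean/true | Omission: median/true |
|---|---|---|---|---|
| 30% | Φ(1.357) = 0.913 | 0.91 | 0.913/0.7 = 1.30 | 1.38 |
| 50% | Φ(0.833) = 0.797 | 0.80 | 0.797/0.5 = 1.60 | 1.75 |
| 80% | Φ(−0.009) = 0.496 | 0.50 | 0.496/0.2 = 2.48 | 2.91 |

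For log-SD 0.5 to 1.5, omission gives 1.21–1.40 times the true mean at 30% BLOQ, 1.38–1.87 at 50% and 1.63–2.78 at 70%. The zero rule gives 0.85–0.98, 0.69–0.93 and 0.49–0.84.

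Under the zero rule the median does not depend on the value substituted while fewer than half the results are BLOQ. Once more than half are BLOQ, it is reported as BLOQ.

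**Step 3: the trailing rule in rectal tissue.** Each participant has two tissue samples per dose: 2 and 48 h (Group 1) or 24 and 72 h (Group 2). A BLOQ at 72 h is trailing if the 24 h sample was quantifiable. If both are BLOQ, there is no last quantifiable concentration and the trailing rule does not reach the result. On the omission reading, two identical 72 h results could then be treated differently: one dropped, the other counted as zero.

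**Step 4: late quantified values.** This rule needs at least two BLOQs followed by a quantified value. It cannot arise in tissue, with two samples per dose. In rectal fluid, with three, the first two would both have to be BLOQ. Blood has seven post-dose samples, so in practice the rule concerns blood.

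**The case against.** The strongest reply is that the zero rule already governs the summaries, and the text gives it good support:

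- It stands in the only paragraph on statistics by nominal time and makes no exception for trailing values.
- The omission sentence speaks of values assigned missing. In the preceding text that wording describes late quantified values, whereas trailing BLOQs are merely treated as missing.
- Provision for BLOQ means, medians and minima presupposes that BLOQ results stay in.
- Ignoring trailing BLOQs is what an AUC to the last measurable concentration requires.

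This stands as the better-supported reading, but it does not close the gap. The trailing sentence lacks the AUC limit that its neighbour carries. Zeros from baseline, early and all-BLOQ results would still give the BLOQ-reporting provisions a use under omission.

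A reader might go further and infer that late concentrations will be overstated. The documents do not support that as settled, because the zero rule biases means downward. Deleting late quantified values would also generally lower a summary in which BLOQ counts as zero.

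Nor do they show that nearly all 24–72 h TAF values are affected. The Protocol's statement that "plasma concentrations of the drug were below the limit of quantification 6-8 hours following dosing" (2.7.2, Oral TAF) concerns oral dosing and plasma. No figure is given for rectal dosing or for rectal matrices.

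A reader might also infer that omission compresses the difference between doses. That would need BLOQ fractions by dose, which are not given, and no formal dose comparison is planned.

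Finally, the study is small and descriptive. SAP 9.1 already lists individual data, LLOQs by matrix, and BLOQ values by assay and time point. That limits the harm, because a reader could rebuild the tables. It does not make the tables unique.

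**Conclusion.** The concern holds as an unresolved conflict between two stated rules, not as a demonstrated upward bias. The factor n/(n−k) between the two possible means is exact: 1.43, 2.0 and 5.0 at 30, 50 and 80% BLOQ. The bias of each rule against the truth (1.30 to 2.48 for omission, 0.91 to 0.50 for zero) rests on the assumed lognormal, CV 100% and BLOQ fractions.

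The default removal of quantified values after consecutive BLOQs is clear in the text, subject to its discretionary qualifier, and matters mainly for blood.

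This should be fixed, because it leaves primary PK tables without a unique definition. It does not threaten the validity of the study.

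**What to change.** In SAP 9.1:

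1. State that treating trailing BLOQ as missing, and excluding late quantified values, applies only to AUC, ke and half-life.
2. State that every assayed sample stays in the concentration tables and figures under the SAP's existing zero rule, including participants whose results are all BLOQ.
3. Show n and number (%) BLOQ at each time point, for each analyte, matrix and dose.
4. Where BLOQ values are present, lead with the median and quartiles, reported as BLOQ when they fall below the LLOQ. The mean can stay as a secondary figure, with a note that it is biased downward.

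LLOQ/2 substitution or a censored-data model for log-scale means is not needed here. After a log transformation, SAP 9.2 reports medians.

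The cost is a few sentences and one table column. Late summaries may look less favourable than they would under omission.
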